## **7.0 DURATION OF FOLLOW UP**

All patients will be followed for 100 days after the last dose of treatment with the agent under this IND or until all treatment related clinical significant toxicities resolve to baseline or grade  $\leq$  1. Adverse events with attribution of possible, probable or definite will be reported following guidelines for adverse event reporting and all SAEs will be reported for 100 days after the last dose. Patients will be followed every 3 months per standard of care for PFS and OS until death, loss to follow up, consent withdrawal, or study termination.

## **8.0 TERMINATION OF TREATMENT AND/OR STUDY PARTICIPATION**

Patients will be informed that they have the right to withdraw from the study at any time for any reason, without prejudice to their medical care. The investigator also has the right to withdraw patients from the study for safety, behavioral or administrative reasons.

The Investigator will make every reasonable effort to keep each patient in the study unless it is in the patient's best interests to discontinue participation. If a patient is removed from the study or declines further participation, all End of Treatment evaluations should be performed if the patient is willing and able to be assessed. A description of the reason(s) for withdrawal from the study must be recorded on the case report form (CRF). The Investigator should also ensure that all patients are followed up for survival status after the Final Visit.

Patients who discontinue following entry will have relevant information completed and recorded on the CRF. All patients who discontinue because of adverse events or clinically significant laboratory abnormalities should be followed up until they recover or stabilize, and the subsequent outcome will be recorded. If any patient should die during the trial or within 30 days of stopping study treatment, the Investigator will inform the IRB and Sponsor (if applicable). The cause of death should be recorded in detail, within 24 hours, on a serious adverse event (SAE) form and reported to institutional, federal and any other appropriate committees and/or sponsors.

## 9.0 CONCOMITANT AND EXCLUDED THERAPIES

### 9.1 Concomitant Therapy

The patient must be told to notify the investigational site about any new medications he/she takes after the start of the study drug. All medications (other than study drug) and significant non-drug therapies (including blood transfusions) administered during the study should be recorded.

Concomitant therapy includes any prescription medications or over-the-counter preparations used by a patient between the 7 days preceding the screening evaluation and the treatment discontinuation visit. Medications taken within 14 weeks prior to study treatment administration must be recorded on the case report form (CRF). Document vaccine use for 30 days prior to first dose of study drug.

Patients who experience infusion-associated symptoms may be treated symptomatically with antipyretics (ibuprofen preferred), diphenhydramine, and/or famotidine or another H2 receptor antagonist, as per standard practice. Serious infusion-associated events manifested by dyspnea, hypotension, wheezing, bronchospasm, tachycardia, reduced oxygen saturation, or respiratory distress should be managed with supportive therapies as clinically indicated (e.g., supplemental oxygen and  $\beta_2$ -adrenergic agonists).

Systemic corticosteroids and TNF $\alpha$  inhibitors may attenuate potential beneficial immunologic effects of treatment but may be administered at the discretion of the treating physician. If feasible, alternatives to corticosteroids should be considered. Premedication may be administered for Cycles  $\geq 2$  at the discretion of the treating physician. The use of inhaled corticosteroids and mineralocorticoids (e.g., fludrocortisone) for patients with orthostatic hypotension or adrenocortical insufficiency is allowed. Megastrol administered as appetite stimulant is acceptable while the patient is enrolled in the study.

Patients who use hormone-replacement therapy, prophylactic or therapeutic anticoagulation therapy (such as low-molecular-weight heparin or warfarin at a stable dose level), or other allowed maintenance therapy should continue their use, unless prohibited.

### 9.2 Prohibited Treatments

The following medications are prohibited during the study (unless utilized to treat a drug-related AE):

- Concomitant use of strong inhibitors of CYP3A4 and/or CYP1A2 or strong inducers of CYP3A4 and/or CYP1A2 (see Appendix 11)
- Immunosuppressive agents (except used to treat a drug-related AE)

- Immunosuppressive doses of systemic corticosteroids (exceptions: participants are permitted the use of topical, ocular, intra-articular, intranasal, and inhalational corticosteroids [with minimal systemic absorption]. Adrenal replacement steroid doses > 10 mg daily prednisone are permitted. A brief [less than 3 weeks] course of corticosteroids for prophylaxis (eg, contrast dye allergy) or for treatment of non-autoimmune conditions [eg, delayed type hypersensitivity reaction caused by a contact allergen] is permitted.)
- Any concurrent anti-neoplastic therapy (i.e., chemotherapy, hormonal therapy, immunotherapy, non-palliative radiation therapy, or standard or investigational agents for treatment of malignancy)
- Any botanical preparation (e.g., herbal supplements or traditional Chinese medicines) intended to treat the disease under study or provide supportive care. Please see restrictions on use of marijuana in section 9.3.
- Prophylactic antimicrobial therapy
- Any live / attenuated vaccine (e.g. varicella, zoster, yellow fever, rotavirus, oral polio and measles, mumps, rubella [MMR]) during treatment and until 100 days post last dose.

### 9.3 Restricted Treatments

Restricted therapies are not prohibited but are not recommended; Investigators should consider possible benefit/risk implications of enrolling and treating participants in whom the following are clearly medically indicated:

- Grapefruit and Seville oranges and their juices can inhibit CYP3A4 (see Appendix 11) and should not be consumed while on treatment.
- Concurrent use of moderate inhibitors or inducers of CYP3A4 and/or CYP1A2 may affect the systemic exposure of BMS-986205. See Appendix 11 for a list of CYP3A4 and CYP1A2 modulators.
- Concurrent smoking (tobacco, marijuana, etc.) may induce CYP1A2 and decrease the systemic exposure of BMS-986205.
- Caution is warranted when consuming marijuana by means other than smoking as it may lead to increased exposure of BMS-986205 through interaction with metabolic enzymes.
- Caution is warranted when administering BMS-986205 to participants taking drugs that are highly dependent on CYP3A4 or CYP2B6 for metabolism. See Appendix 11 for a list of sensitive CYP3A4 and CYP2B6 substrates.
- Caution is warranted when administering BMS-986205 to participants taking drugs that may be associated with QT prolongation. See Appendix 13 for a list of common medications associated with QT prolongation.

- Caution is warranted when administering BMS-986205 to participants taking drugs that are subject to extensive intestinal efflux by P-gp/BCRP. See Appendix 14 for a list of common P-gp/BCRP substrates.
- In vitro solubility data indicate that BMS-986205 has decreased solubility with increasing pH. Participants should avoid taking proton pump inhibitors during the treatment period if possible. H2 antagonists and short-acting antacid agents may be taken, but it is recommended that these not be taken 4 hours before or 4 hours after dosing of BMS-986205.
- Caution is warranted when using other agents known to cause methemoglobinemia (see Appendix 15). Dapsone, topical anesthetics, and antimalarial drugs are the most likely agents, and thus these medications should only be used after discussion with the Principal Investigator.

#### **9.4 Other Restrictions and Precautions**

Use caution and monitor for symptoms of serotonin syndrome in participants receiving concurrent serotonergic psychiatric medications and/or tryptophan supplements.

#### **9.5 Permitted Therapy**

Participants are permitted the use of topical, ocular, intra-articular, intranasal, and inhalational corticosteroids (with minimal systemic absorption). Adrenal replacement steroid doses  $> 10$  mg daily prednisone are permitted. A brief (less than 3 weeks) course of corticosteroids for prophylaxis (eg, contrast dye allergy) or for treatment of non-autoimmune conditions (eg, delayed type hypersensitivity reaction caused by a contact allergen) is permitted.

## 10.0 STUDY CALENDAR

Evaluation	Pre-Treatment		Treatment Cycles	End of Treatment		Post-Treatment	
Treatment Cycle / Title	Screening		Day 1 of Each Cycle 	End of Treatment 	Safety Visit 	Follow Up 	Day 100 Visit 
Scheduling Window	≤28 days prior to registration	≤14 days prior to registration	± 3 days	± 7 days	± 7 days	± 7 days	± 7 days
History							
Informed Consent	X						
Medical History	X						
Clinical/Laboratory/Assessments							
Physical Exam  : height  , weight, BSA  , performance status 		X	X		X	X	
Vital signs 		X	X		X	X	
Adverse Events and Concomitant Medications 	X		Continuously				X
Hematology: CBC with differential		X	X		X		
Biochemistry 		X	X		X		
AFP, TSH, hepatitis viral load if applicable		X	X 				
G6PD 		X					
Methemoglobin and Oxygen Saturation 		X	X				
HIV, HBV, HCV serology		X					
Pregnancy test if applicable 		X	X				
ECG		X		X			
Chest/abdomen/pelvis CT scan (MRI if appropriate)	X 		X 				
Correlatives							
Correlative Samples: Plasma, Serum, Whole Blood		X 	X 				
Tumor Tissue		X 	X 				
Stool sample		X					
Study Treatment Administration							
Nivolumab			X				
BMS-986205			daily				

Evaluation	Pre-Treatment	Treatment Cycles	End of Treatment	Post-Treatment

 
1. Complete physical examination at screening only; subsequent physical examinations are limited to signs and symptoms of disease or toxicity. Clinical tumor measurements (if applicable).
 
2. Height is required at Baseline only.
 
3. BSA should be calculated prior to each dose of treatment.
 
4. ECOG only.
 
5. Vital signs: temperature, systolic and diastolic blood pressure, respiratory rate, and pulse.
 
6. Biochemistry: creatinine (serum), sodium, potassium, total bilirubin, alkaline phosphatase, AST, ALT, albumin, INR
 
7. Quantitative or qualitative G6PD assay must be performed within 28 days prior to enrollment to screen for underlying G6PD deficiency.
 
8. Methemoglobin levels must be performed within 14 days prior to enrollment, C1D1, each treatment cycle or more frequently if clinically indicated based on symptoms. Methemoglobin levels to be assessed on arterial or venous blood sample or by co-oximetry. Oxygen saturation levels must be measured within 14 days prior to C1D1 and every cycle while on treatment by pulse oximetry at rest.
 
9. Female subject of child-bearing potential must have a negative serum or urine pregnancy test (minimum sensitivity 25 IU/L or equivalent units of human chorionic gonadotrophin [hCG]) within 14 days of C1D1, and <math>\leq</math> 24 hr prior to planned treatment initiation, and prior to each cycle while on treatment. Women with childbearing potential and males must be willing to use adequate birth control on trial and until 5 months for women or 7 months for men after the last of study therapy. Refer to Appendix 9.
 
10. Baseline symptoms will be documented prior to starting study treatment. SAE will be collected starting from time of consent. Adverse Events collection will begin from the time of first dosing through 100 day post-treatment. Adverse events will be coded as per CTCAE V5.0.
 
11. <math>\leq</math> 28 days prior to registration.
 
12. One cycle consists of 2 weeks.
 
13. Every other cycle. If TSH <math>>2</math> x ULN, check free T3 and T4.
 
14. Radiology to be repeated at the following time points (<math>\pm</math> 7 days): at the end of 8 and 16 weeks, then every 12 weeks, and at End of Treatment. Patients that go off treatment without radiological progression will have scans repeated every 3 months until documented disease progression or start of new therapy.
 
15. Blood samples for correlative studies will be obtained at the following time points (<math>\pm</math> 7 days): day 15, day 29, day 57, day 85 and end of treatment. Core biopsy of tumor will be obtained at Baseline (unless there is adequate archival tumor specimen available), day 29 (<math>\pm</math> 7 days), and End of Treatment (end of treatment biopsy is optional).
 
16. End of Treatment is at the time the decision is made to take the patient off study treatment.
 
17. Safety Visit: 28 days after taken off protocol treatment.
 
18. Follow up: Every 3 months from End of Treatment for survival follow up.
 
19. 100 day visit for safety follow up.
 
				

## 11.0 STUDY EVALUATIONS

### 11.1 Screening Phase

The screening phase is defined as the interval between the day the subject signs the informed consent (ICF) and the day of registration. The screen phase will allow a total of 28 days. The subject can re-screen if he/she fails the first screen due to temporary illness.

### 11.2 Treatment Phase

One cycle of treatment is 14 days in which the subject will receive the combination therapy and the treatment phase is up to a total of 24 months. The subject may stop both therapy at 24 months or continue therapy per treating physicians based on standard of care.

### 11.3 End of Treatment Visit

The end of treatment visit should be performed when the treating physician decides to permanently discontinue study drug combinations.

### 11.4 Follow-up Phase

The safety follow up phase is the interval between the end of treatment visit and scheduled safety follow up visit which will occur 28 ( $\pm 7$  days) days after discontinuation of combination therapy. If the subject starts on a new anticancer drug before 28 ( $\pm 7$  days) days after discontinuation of study drugs, the safety follow up visit should be prior to the start of new therapy. If the subject discontinues treatment without disease progression, the subject will be followed every 84 days (12 weeks  $\pm 7$  days) by imaging to monitor disease status. Once the subject starts a new therapy or has progression of disease, the subject's survival status should be followed with telephone or email until death or withdrawal of consent.

### 11.5 Efficacy

Response and progression will be evaluated in this study using the new international criteria proposed by the revised Response Evaluation Criteria in Solid Tumors (RECIST) guideline (version 1.1) [35] as well as iRECIST criteria. Changes in the largest diameter (unidimensional measurement) of the tumor lesions is used in the RECIST criteria. Radiologic assessment is to be repeated at the following time points (+/- 7 days): at the end of 8 and 16 weeks, then every 12 weeks, and at End of Treatment. Patients that go off treatment without radiological progression will have scans repeated every 3 months until documented disease progression or start of new therapy.

### **11.5.1 Disease Parameters**

#### **11.5.1.1 Measurable Disease**

The presence of at least one measurable lesion. If the measurable disease is restricted to a solitary lesion, its neoplastic nature should be confirmed by cytology/histology.

#### **11.5.1.2 Measurable Lesions**

Lesions that can be accurately measured in at least one dimension with longest diameter 20mm using conventional techniques or 10mm with spiral CT scan.

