## 4.0 SUBJECT SELECTION

### 4.1 Inclusion Criteria

Patients must meet all of the following criteria to be eligible for study entry.

1. Men and women  $\geq 18$  years of age at the time of study entry.
2. Willing and able to provide written informed consent for the trial.
3. Life expectancy  $>12$  weeks.
4. Histologically or imaging confirmed hepatocellular carcinoma (mixed hepatocellular/cholangiocarcinoma or fibrolamellar subtypes are excluded).
5. Have disease that is not amenable for curative treatment approach.
6. Have measurable disease based on RECIST v1.1.
7.  $\geq 1$  liver lesions accessible for core biopsy that was either not previously treated by liver-directed therapy or progressed following liver-directed therapy.
8. Child-Pugh score of A.
9. ECOG performance status of 0 or 1.
10. Adequate hematology parameters:
  - a. Absolute neutrophil count (ANC)  $\geq 1000$  cell/mm $^3$
  - b. Platelet count  $\geq 50,000$ /mm $^3$
  - c. Hemoglobin (Hgb)  $\geq 8$  g/dL
11. Acceptable blood chemistry levels:
  - a. AST/SGOT, ALT/SGPT  $\leq 5$  x upper limit of normal (ULN)
  - b. Total bilirubin  $\leq 2$  ULN
  - c. Creatinine  $\leq 2$  x ULN
12. Subjects with active hepatitis B virus (Hep B) are allowed if antiviral therapy for hepatitis B has been given for  $>8$  weeks and viral load is  $<100$  IU/ml prior to first dose of trial treatment. Subjects with untreated hepatitis C virus (HCV) are allowed.
13. Willingness to undergo mandatory pre-treatment biopsy (unless there is adequate archival tumor specimen available) and mandatory on-treatment biopsy.

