#### **11.5.1.3 Non-Measurable Lesions**

All other lesions, including small lesions (longest diameter <20 mm with conventional techniques or <10 mm with spiral CT scan), i.e., bone lesions, ascites, pleural/pericardial effusion, cystic lesions, and abdominal masses that are not confirmed and followed by imaging techniques.

All measurements should be taken and recorded in metric notation, using a ruler or calipers. All baseline evaluations should be performed as closely as possible to the beginning of treatment, preferably within two weeks of treatment initiation, and never more than 4 weeks before the beginning of the treatment.

The same method of assessment and the same technique should be used to characterize each identified and reported lesion at baseline and during follow up.

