### **11.5.2 Methods of Measurements**

CT and MRI are the best currently available and reproducible methods to measure target lesions selected for response assessment. Conventional CT and MRI should be performed with cuts of 10 mm or less in slice thickness contiguously. Spiral CT should be performed using a 5 mm contiguous reconstruction algorithm. This applies to tumors of the chest, abdomen and pelvis. Head and neck tumors and those of extremities usually require specific protocols.

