## Appendix 12: Immune RECIST Criteria

	RECIST 1.1	iRECIST
Definitions of measurable and non-measurable disease; numbers and site of target disease	Measurable lesions are $\geq 10$ mm in diameter ( $\geq 15$ mm for nodal lesions); maximum of five lesions (two per organ); all other disease is considered non-target (must be $\geq 10$ mm in short axis for nodal disease)	No change from RECIST 1.1; however, new lesions are assessed as per RECIST 1.1 but are recorded separately on the case report form (but not included in the sum of lesions for target lesions identified at baseline)
Complete response, partial response, or stable disease	Cannot have met criteria for progression before complete response, partial response, or stable disease	Can have had iUPD (one or more instances), but not iCPD, before iCR, iPR, or iSD
Confirmation of complete response or partial response	Only required for non-randomised trials	As per RECIST 1.1
Confirmation of stable disease	Not required	As per RECIST 1.1
New lesions	Result in progression; recorded but not measured	Results in iUPD but iCPD is only assigned on the basis of this category if at next assessment additional new lesions appear or an increase in size of new lesions is seen ( $\geq 5$ mm for sum of new lesion target or any increase in new lesion non-target); the appearance of new lesions when none have previously been recorded, can also confirm iCPD
Independent blinded review and central collection of scans	Recommended in some circumstances—eg, in some trials with progression-based endpoints planned for marketing approval	Collection of scans (but not independent review) recommended for all trials
Confirmation of progression	Not required (unless equivocal)	Required
Consideration of clinical status	Not included in assessment	Clinical stability is considered when deciding whether treatment is continued after iUPD

"i" indicates immune responses assigned using iRECIST. RECIST=Response Evaluation Criteria in Solid Tumours. iUPD=unconfirmed progression. iCPD=confirmed progression. iCR=complete response. iPR=partial response. iSD=stable disease.

Table 1: Comparison of RECIST 1.1 and iRECIST

	Timepoint response with no previous iUPD in any category	Timepoint response with previous iUPD in any category*
Target lesions: iCR; non-target lesions: iCR; new lesions: no	iCR	iCR
Target lesions: iCR; non-target lesions: non-iCR/non-iUPD; new lesions: no	iPR	iPR

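### Section 11.5 claims RECIST 1.1, but its response table ignores non-target lesions and its lesion-size rules differ from Appendix 12, so one extra responder could enter the primary ORR

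*Combined protocol and SAP*

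**What the plan says.** Criterion 6 in Section 4.1 reads "Have measurable disease based on RECIST v1.1". The primary objective in Section 2.1 is ORR by RECIST 1.1, and Section 11.5 opens by adopting version 1.1 together with iRECIST.

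**Lesion size.** Section 11.5.1.2 counts as measurable "Lesions that can be accurately measured in at least one dimension with longest diameter 20mm using conventional techniques or 10mm with spiral CT scan". Section 11.5.1.3 mirrors this for non-measurable lesions: "longest diameter <20 mm with conventional techniques or <10 mm with spiral CT scan". Neither has a separate threshold for lymph nodes, and nothing in Section 11.5 limits the number of target lesions. Section 11.5.2 adds "Conventional CT and MRI should be performed with cuts of 10 mm or less in slice thickness contiguously" and gives spiral CT its own sentence. The study calendar asks for CT, with MRI where appropriate.

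The RECIST 1.1 column of Appendix 12 says instead: "Measurable lesions are $\geq 10$ mm in diameter ( $\geq 15$ mm for nodal lesions". It goes on: "maximum of five lesions (two per organ); all other disease is considered non-target". It makes no split by imaging technique, and its iRECIST column leaves these definitions unchanged.

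**Overall response.** Section 11.5.3.1 defines PD as a 20% increase in the target sum or a new lesion. Table 2 in 11.5.3.2 derives overall response from two inputs, target lesions and new lesions. Neither mentions non-target disease. The second table in Appendix 12 uses three inputs: target, non-target and new lesions.

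**The concern.** The protocol names one standard and then writes out working rules that differ from its own summary of that standard. A reader scoring scans from Section 11.5 and a reader using Appendix 12 can reach different answers on the same images.

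The response table matters most. It applies to any patient with non-target disease, whatever the scanner or lesion size, and one of its errors runs towards counting a response. The decision rule in Section 14.1 is at least 1 response in 9, then at least 3 in 17, so a single patient can decide either stage. Section 11.5.3.3 also lets unconfirmed responses carry the trial through the interim, so a required second scan does not act as a check there.

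The size rules bear on which lesions are followed and, less often, on who is eligible.

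**Working it through.** **1. The plan's own design.** The inputs are n1 = 9, continue with at least 1 response, n = 17, success with at least 3, p0 = 5%, p1 = 25%, one-sided 0.05 and 80% power (Sections 3.0, 14.1 and 14.2). The Study Schema prints a different set of Simon parameters, which is not used here. With q = 1 - p,

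P(success) = 1 - q^9 - 9·p·q^16 - 108·p²·q^15.

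The three subtracted terms are: no response in stage 1; exactly one response in all, in stage 1; and exactly two in all, at least one of them in stage 1. The coefficient 108 is C(17,2) - C(8,2) = 136 - 28.

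- p = 0.05: 1 - 0.6302 - 0.1981 - 0.1251 = 0.0466
- p = 0.25: 1 - 0.0751 - 0.0226 - 0.0902 = 0.8122

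The stated alpha and power reproduce, and the lesion definitions do not change them.

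**2. Overall response, side by side (no new lesion).**

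| Target | Non-target | Section 11.5, Table 2 | Appendix 12 table | Effect on ORR |
|---|---|---|---|---|
| PR | progression | PR | iUPD | can add a responder |
| CR | persisting, not progressing | CR | iPR | none; both count as response |
| SD | progression | SD | iUPD | none; affects DCR and PFS |

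The Appendix 12 table is for iRECIST. Its footnote says lesions are defined on RECIST 1.1 principles, and that the CR, PR and SD categories coincide under both systems unless there is pseudoprogression. Its rows also refer to a RECIST 1.1 criterion of unequivocal progression in non-target disease. The appendix therefore treats non-target status as part of both systems.

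The first row adds a responder only when non-target progression comes before or with the first target PR. A patient who reached PR earlier is already a responder under either text.

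**3. Lesion size, side by side.**

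| Lesion | Section 11.5 | Appendix 12 |
|---|---|---|
| Non-nodal, 10 mm or more, spiral CT | measurable | measurable |
| Non-nodal, 10-19 mm, conventional CT | not measurable | measurable |
| Node, 10-14 mm, spiral CT | measurable | not measurable |
| Non-nodal, 10-19 mm, MRI | unclear | measurable |
| Number of targets | no limit | five, two per organ |

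MRI is unclear because the 20 mm rule refers to conventional techniques without defining them. Section 11.5.2 pairs MRI with conventional CT, but only for slice thickness.

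**4. What one patient is worth.** 1/17 = 5.9 points; 2/17 = 11.8% fails and 3/17 = 17.6% passes. The chance of finishing with exactly three responses after passing stage 1 is 624·p³·q^14, where 624 = C(17,3) - C(8,3) = 680 - 56. This gives 0.220 at a true ORR of 20% and 0.174 at 25%. At p0 = 5%, the chance of finishing with exactly two, where one added response would turn failure into success, is 108·0.05²·0.95^15 = 0.125. These figures show how often the result sits at the boundary. They are not misclassification rates.

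**5. Illustration under an assumption.** Suppose the true rate is 5% and Table 2 adds a false responder in a share f of patients, so that the recorded rate is 5% + f. The formula in step 1 then gives a false-positive rate of:

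- f = 0: 4.7%
- f = 1 point: 1 - 0.5730 - 0.2007 - 0.1537 = 7.3%
- f = 5 points: 1 - 0.3874 - 0.1668 - 0.2224 = 22.3%

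The documents give no value for f, so the range shows sensitivity only.

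**The case against.** The strongest reply is that the governing standard is already named. Criterion 6, the primary objective and the opening of Section 11.5 all say RECIST 1.1, and Appendix 12 labels its column that way. A careful reader has grounds to treat 11.5.1.2-11.5.1.3 as leftover text. That stands in part: it shows which text should prevail. It does not remove the conflict, because Section 11.5 is the operative efficacy section and nothing in it says that Appendix 12 overrides it.

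Three further limits stand:

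- On spiral CT both texts use 10 mm for non-nodal lesions, and criterion 7 requires a biopsy-accessible liver lesion, so few patients would enter on nodes alone.
- A different size threshold changes which lesions enter the sum. It does not by itself create a response, and Section 11.5.1.3 requires the same technique at baseline and follow-up.
- Appendix 12 does handle non-target progression, although in the iRECIST table, while the primary ORR is by RECIST 1.1.

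A reader might go further and infer that every 10-19 mm MRI lesion is non-measurable under Section 11.5, so that eligible patients would be turned away. The documents do not support that. MRI is never classed as a conventional technique for measurability, and refusal would also require a site to apply 11.5.1.2 over criterion 6. A reader might also take the 17-22% boundary figures as the chance of a wrong conclusion. They are not, because they say nothing about how often a response is misread.

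**Conclusion.** The concern holds as a conflict within the protocol. Its more serious part is Table 2 with the PD definition in 11.5.3.1: as written, they score a target PR with non-target progression as PR, and a target CR with persisting non-target disease as CR. Only the first can change the primary ORR. It moves the ORR by 5.9 points per patient, in a design where one patient decides success at the boundary.

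The size-rule conflict is real for lesions on conventional CT, for small nodes on spiral CT and for the number of targets. It is unresolved for MRI. Its effect on eligibility is probably small.

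The number of affected patients is not given, so no error rate can be attached to either part. The sample size, alpha and power are unaffected. The conclusion assumes that the Appendix 12 footnote carries its non-target logic over to RECIST 1.1. This should be corrected before scans are read for the primary analysis.

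**What to change.** - State in Section 11.5 that the RECIST 1.1 definitions summarised in Appendix 12 govern criterion 6 and the primary ORR.
- Replace 11.5.1.2-11.5.1.3 with those definitions: 10 mm for non-nodal lesions, 15 mm for nodes, and at most five targets with two per organ. Say explicitly how MRI is treated and which axis is measured for nodes, since the measurable-lesion entry in Appendix 12 names no modality and gives no axis with its 15 mm threshold.
- Align the sum of longest diameters in 11.5.3.1 with the chosen nodal axis.
- Add non-target status to 11.5.3.1 and as a column in Table 2, so that non-target progression gives overall PD and a target CR with persisting non-target disease is not CR.

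The cost is protocol wording, with no extra scans, readers or patients. A few responses may be reclassified downward.
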